5.2.2.2 Estimand Framework for Investigators Assessment of Clinical Response

	Investigators Assessment of Clinical Response	
Population	ITT and CE-PTE Populations	
Variable/Endpoint	Investigator Assessment of Clinical Success	
Handling of intercurrent	Composite estimand as the following ICE's are	
events	incorporated into the variable/endpoint:	
	• Receipt of alternative (rescue) therapy (failure)	

The four attributes of estimand are described below:

	 Receipt of antibiotic that may be effective for CABP for a different infection (failure) Death (failure) 	
Population-level summary	Difference between treatment groups in percentage of subjects with an investigators assessment clinical sucess	

5.2.2.3 Microbiologic Outcomes

Microbiological response definitions for the evaluations performed at the EOT and PTE Visits and analyzed in the microITT and microbiologically evaluable (ME) populations are presented in the table below. Post-baseline microbiological samples will be collected only as clinically indicated. Atypical pathogens identified only by acute and convalescent serology or baseline urinary antigen tests (UAT), and *Streptococcus pneumoniae* identified only by baseline UAT can only have a presumed or indeterminate microbiologic response.

If a subject has the same pathogen (ie, same genus and species) identified from both a respiratory and blood specimen, a microbiological response is determined for each of the pathogens. The microbiologic response for the respiratory pathogen is based on the pathogen isolated from the EOT or PTE specimen, if a specimen was collected. The microbiologic response for the blood pathogen is based on the blood sample collected at EOT or PTE, or if a sample was not collected at the post-baseline visit, the blood sample collected prior to and closest to the visit. For the pathogen specific microbiologic response, the worst outcome for the pathogen should be summarized. If *Streptococcus pneumoniae* is identified from both a UAT and a culture, the culture should be used to determine microbiological response.

Term	Definition	
Eradication	The baseline pathogen based on culture was absent from repeat culture(s) of the same sample type (blood or respiratory specimen).	
Presumed Eradication	No post-baseline source specimen to culture in a subject assessed with a clinical success by the Investigator	
Persistence	The baseline pathogen based on culture was present in repeat culture(s) of the same sample type (blood or respiratory specimen).	
Presumed Persistence	No post-baseline source specimen to culture in a subject assessed with a clinical failure by the Investigator	
Indeterminate	The subject's clinical response is indeterminate or other circumstance that precludes a microbiological evaluation	

Table 5.Per-Pathogen Microbiological Response Definitions at the EOT and PTE
Visits

Abbreviations: EOT = end of treatment; PTE = post-therapy evaluation.

Microbiological outcomes are further categorized as favorable, unfavorable, and indeterminate. Favorable microbiological outcomes are defined as eradication or presumed eradication. Unfavorable microbiological outcomes are defined as persistence or presumed persistence. Microbiological response will be derived using electronic microbiology data from the central laboratory and from pathogen determination provided by the Sponsor for each baseline isolate.

Overall microbiological response at PTE is determined as follows from the microbiological responses at the EOT and PTE Visits:

EOT Visit	PTE Visit	Overall Microbiologic Response at PTE
Favorable	Favorable	Favorable
Favorable	Unfavorable	Unfavorable
Favorable	Indeterminate	Indeterminate
Unfavorable	Favorable	Unfavorable
Unfavorable	Unfavorable	Unfavorable
Unfavorable	Indeterminate	Unfavorable
Indeterminate	Favorable	Indeterminate
Indeterminate	Unfavorable	Unfavorable
Indeterminate	Indeterminate	Indeterminate

Table 6.	Per-Pathogen	Microbiologic	Response
	I CI I acmogen	inter oprotogie	response

Abbreviations: EOT = end of treatment; PTE = post-therapy evaluation.

Note: Favorable is defined as eradication or presumed eradication. Unfavorable is defined as persistence or presumed persistence.

Per-subject responses will be based on per-pathogen responses. To have an overall per-subject favorable microbiologic response, the outcome for each baseline pathogen must be favorable (eradicated or presumed eradicated). If the outcome for any pathogen is unfavorable (persistence or presumed persistence), the subject will be considered to have an unfavorable per-subject microbiologic response. Subjects with an indeterminate response for all pathogens will be considered to have an indeterminate per-subject microbiologic response. If the same pathogen is isolated from multiple sample types (blood, respiratory, urine), the worst outcome will be used to determine per-subject microbiologic response. Superinfections will not be considered in the microbiological response. Microbiological response from worst to best are as follows: persistence, presumed persistence, indeterminate, presumed eradication, and eradication.

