## 7.14 Permitted Treatments

All other treatments not specified as prohibited are permitted during the study. Subjects requiring additional or alternative antibacterial therapy for their CABP will be judged as Clinical Failures and test article will be discontinued. Further treatment for their infection is at the discretion of the investigator or the subject's health care provider and will be considered as a concomitant medication.

Subjects should be encouraged to contact site personnel before starting any new treatment.

For all treatments received by the subject during the study, relevant information must be recorded on the subject's eCRF.

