#### 8.13.1.2 Investigator's Assessment of Clinical Response at EOT

End of treatment assessments should be performed on the calendar day of, or within 2 days following the last dose of any test article. If a subject withdraws prematurely or terminates participation in the study prior to completion of the planned antibiotic therapy, the EOT visit should be conducted.

The investigator will determine which of the following clinical outcomes the subject meets based on the criteria below (must select 1 outcome):

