#### 8.13.1.3 Investigator's Assessment of Clinical Response at PTE

The PTE assessment is to be performed 5 to 10 days after the subject's last day of therapy. The investigator will determine which of the following clinical outcomes the subject meets based on the criteria below (must select 1 outcome):

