### 8.14 Microbiologic Response

#### 8.14.1 Respiratory Culture and Gram Stain

At the Screening visit collection of an adequate quality expectorated or induced sputum or other respiratory specimen reflecting fluid from the lower respiratory tract (eg, respiratory fluid obtained by bronchoalveolar lavage or bronchoscopy; pleural fluid obtained by thoracentesis; or expectorated or induced sputum meeting adequacy criteria) should be attempted from all subjects and submitted to the local microbiology laboratory for Gram stain and culture (see Appendix 1). The date, time and type of specimen submitted will be recorded on source documents at the local laboratory. These specimens may be obtained as part of routine, non-study evaluation of a subject being evaluated for CABP and therefore could be obtained prior to obtaining informed consent.

An adequate quality sputum specimen will be defined as having the following 2 findings as reported by the local laboratory:

- 1. < 10 Squamous epithelial cells/low power field (LPF) (ie,  $100 \times$ )
- 2. > 25 Polymorphonuclear cells/LPF (ie,  $100 \times$ )

Adequate quality sputum specimens and other Screening respiratory specimens for culture should be obtained prior to first dose of test article. In the event that a sputum specimen is determined to be inadequate or cannot be obtained prior to the first dose of test article, collection of a specimen should be attempted within 24 hours after the first dose of test article. As the infection responds to therapy, obtaining repeated specimens for culture or examination may not be clinically appropriate and/or there may be no material for culture. At the EOT and/or PTE visit, respiratory specimen cultures and Gram stains should be obtained only for subjects who are Clinical Failures and require alternative antibacterial treatment for CABP.

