- e To be conducted on the day of, or within 2 days following the last dose of test article. Should also be conducted for any prematurely withdrawn subject on the day of, or within 2 days following the last dose of test article.
- f The Final Follow-up assessment may be conducted via telephone contact or by another interactive technology for subjects who were considered to be Clinical Successes and had no ongoing AEs, clinically significant laboratory findings or ECG abnormalities noted at or after the PTE visit. Otherwise, the visit must be conducted in person. Home nursing can be considered for EOT, PTE, and in person FFU visits, if deemed necessary and approved by Sponsor. Page 75 of 85

Confidential and Proprietary

g Written and signed ICF must be obtained before any study assessment is performed.

- h The investigator should assess the severity of the subject's CABP symptoms of cough, sputum production, pleuritic chest pain, and dyspnea based upon the Community-Acquired Bacterial Pneumonia Subject Symptom Severity Guidance Framework for Investigator Assessment (Appendix 3).
  i Subjects must have a confirming CXR or CT scan consistent with acute bacterial pneumonia within the 48 hours prior to the first dose of test article.
- j Only subjects with a PORT Risk Class of III or IV are eligible for enrollment.
- k Local laboratory hematology and chemistry evaluations required for assessing subject eligibility..

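### SAP Table 5 lets a negative culture taken on rescue antibiotics count as Eradication, while the same clinical failure without a specimen counts as Presumed Persistence

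*SAP*

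**What the plan says.** SAP 5.2.2.3, Table 5, gives Eradication when "The baseline pathogen based on culture was absent from repeat culture(s) of the same sample type (blood or respiratory specimen"). The investigator's clinical outcome enters only when nothing was cultured. Presumed Persistence, for instance, is "No post-baseline source specimen to culture in a subject assessed with a clinical failure by the Investigator". The section then adds: "Favorable microbiological outcomes are defined as eradication or presumed eradication".

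Protocol 8.14.1 says who is cultured at EOT and PTE: "respiratory specimen cultures and Gram stains should be obtained only for subjects who are Clinical Failures and require alternative antibacterial treatment for CABP". Footnote v of the schedule in both documents repeats this.

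On timing, Protocol 7.14 states: "Subjects requiring additional or alternative antibacterial therapy for their CABP will be judged as Clinical Failures and test article will be discontinued". EOT assessments take place "on the calendar day of, or within 2 days following the last dose of any test article" (Protocol 8.13.1.2), and for PTE, "The PTE assessment is to be performed 5 to 10 days after the subject's last day of therapy". SAP 7.6 uses EOT and PTE data in the micro-ITT analyses whenever those visits took place. Neither document requires the specimen to precede the first rescue dose, or sets aside a culture taken after it.

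**The concern.** The planned post-baseline respiratory cultures come almost entirely from subjects who are changing, or have changed, to another antibacterial. A negative culture on an active rescue drug says little about what test article did, yet Table 5 treats it as proof of eradication. The plan's clinical estimands (SAP 5.2.1.1 and 5.2.2.2) go the other way and count rescue as failure. No intercurrent-event rule is given for microbiological response.

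At stake are the per-subject and per-pathogen favorable rates at EOT and PTE, in the micro-ITT and ME populations. SAP 6.1.4.3 keeps subjects rescued for insufficient effect in CE, and therefore in ME if a baseline pathogen was found. For these subjects, the recorded result can turn on whether the site obtained a specimen.

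**Working it through.** **1. The rules applied to a subject who is a clinical failure at PTE** (SAP Tables 5 and 6; negative cultures assumed to be taken on rescue)

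| EOT: clinical / culture | PTE: clinical / culture | EOT result | PTE result | Overall at PTE |
|---|---|---|---|---|
| Success / none | Failure / negative | Favorable | Favorable | **Favorable** |
| Success / none | Failure / none | Favorable | Unfavorable | Unfavorable |
| Failure / negative | Failure / negative | Favorable | Favorable | **Favorable** |
| Failure / negative | Failure / none | Favorable | Unfavorable | Unfavorable |
| Failure / none | Failure / negative | Unfavorable | Favorable | Unfavorable |
| Failure / positive | Failure / negative | Unfavorable | Favorable | Unfavorable |

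Rows 1 and 2 differ only in whether a specimen was taken. SAP Table 4 makes both subjects clinical failures at PTE. Rows 5 and 6 show Table 6 closing the route once EOT is Unfavorable. Rows 3 and 4 are Favorable in the EOT analysis itself if the EOT culture followed the first rescue dose.

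**2. Blood.** Where no blood sample was collected at the visit, SAP 5.2.2.3 uses the closest earlier one. Protocol 8.12.2.2 has positive blood cultures repeated until negative. Neither rule stops at rescue. The SAP states its rule for a pathogen found in both blood and a respiratory specimen, where the worse result applies. The route therefore matters mainly if the rule is also applied to a pathogen found in blood alone; row 4 could then become Favorable.

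**3. Scale.** The plan's own figure reproduces: 0.30 × 670 = 201 micro-ITT subjects, or 201 / 2 = 100.5 per arm. One reclassified subject is 1 / 100.5 = 1.0 point in that arm.

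**4. Illustrative total.** Formula: failure rate × share culture-identified × share of those culture-negative on rescue.
- Failure rate 7.5% to 15%. The low end is 100 − 92.5, from the omadacycline CE result at PTE in CABP-1200. The high end is 100 − 85, from the sample-size assumption for PTE in ITT. That ITT figure also counts indeterminates as non-success.
- Share culture-identified: one half. This is an assumption. It is needed because SAP 5.2.2.3 allows only a presumed or indeterminate response for pathogens identified solely by urinary antigen or serology.
- Share culture-negative on rescue: 20% to 40%. This is an assumption; the documents give no figure.

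Low: 0.075 × 0.5 × 0.20 = 0.0075, which is 0.75 points, or 201 × 0.0075 = 1.5 subjects.
High: 0.15 × 0.5 × 0.40 = 0.03, which is 3.0 points, or 201 × 0.03 = 6.0 subjects.

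Both are before Table 6 removes some paths from the overall PTE response.

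**The case against.** **The EOT culture is planned for about the moment of the switch.** Protocol 7.6.3 says that the decision to stop test article prompts the EOT evaluation, and Protocol 9.3 puts the procedures on that day. This stands. A reader might infer from the window in Appendix 1 ("To be conducted on the day of, or within 2 days following the last dose of test article") that rescue has usually begun by the EOT culture, but the documents do not show that. The window permits it, and no order is set for sampling and first rescue dose on the same day. The PTE route is unaffected.

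**Table 5 has an exit.** Its Indeterminate category covers other circumstances that prevent a microbiological evaluation. It does not mention rescue, and it does not displace the explicit Eradication rule. SAP 7.3 limits Indeterminate to subjects whose clinical response is Indeterminate, although that sentence sits in a bullet about missing specimens and can be read as governing only that case. The two passages need reconciling either way.

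**Clinical and microbiological response are different measures.** A clinical failure may truly have cleared the baseline pathogen, so Presumed Persistence overrides an observed negative and Indeterminate is defensible. This is fair, but the plan already presumes persistence in failures with no specimen, and a negative culture on another active drug adds little about test article. In micro-ITT the choice does not affect the favorable rate, since both categories are non-favorable and stay in the denominator. In ME it matters, because Indeterminate subjects are excluded.

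**The blinded evaluability team could intervene.** SAP 6.2 gives it population criteria and pathogen determination. It states no rule for negative cultures on rescue.

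**The analysis is supportive.** SAP 9.4 makes these intervals descriptive, with no non-inferiority conclusion. This stands and limits the importance of the point.

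**Conclusion.** The concern holds as an omission: the plan sets no cut-off at rescue, and following it literally can score a rescued clinical failure as a microbiological success. For the overall PTE response, the open paths are relapse after EOT with a negative PTE culture, negative cultures at both visits, and possibly the earlier-blood-culture rule. The EOT response is affected only when sampling follows the first rescue dose.

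The size is unknown. About 1 point per affected subject per arm follows from the plan's own numbers. The total of roughly 1–3 points rests on the assumed shares above.

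Three stronger readings are tempting but unsupported. A reader might apply a 10–20% failure rate and a 20–40% negative share to all 201 subjects: 201 × 0.10 × 0.20 = 4 up to 201 × 0.20 × 0.40 = 16 subjects, or 2–8 points. That includes subjects who cannot be scored by culture, and its upper failure rate exceeds the CABP-1200 non-success rates (at most 100 − 85.2 = 14.8%). A reader might infer that a difference between arms is hidden; the documents do not allow the direction or size of any between-arm effect to be worked out. A reader might also take the efficacy conclusions to be in doubt, but ECR and investigator-assessed clinical response do not use these cultures.

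**What to change.** Add to SAP 5.2.2.3 and Table 5: a negative culture collected after the first dose of a non-study systemic antibacterial active against the baseline pathogen cannot establish Eradication. It is handled as if no specimen had been obtained, so the response follows the investigator's clinical outcome and a Clinical Failure becomes Presumed Persistence. A positive culture still counts as Persistence. Apply the same cut-off to the earlier-blood-culture rule. State that this takes precedence over the other-circumstance wording in Table 5, so that the table agrees with SAP 7.3.

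The cost is a short SAP amendment before unblinding and one programming condition. SAP 7.3 already has missing antibiotic times queried, and SAP Appendix 3 covers undetermined antibacterial dates. Specimen timing needs checking: Protocol 8.14.1 describes recording specimen date and time in local-laboratory source documents for Screening specimens, so the sponsor should confirm that the database holds them for EOT and PTE specimens and for repeat blood cultures. The reported favorable rate may be slightly lower.

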By definition, the ME populations (ME-EOT and ME-PTE) must have sufficient information to determine the outcome and thus, excludes subjects with indeterminate responses. For the ME populations, the proportion of subjects with a microbiological response is defined using the following formula:

Number of subjects with eradication + Number of subjects with presumed eradication (Number of subjects with eradication + Number of subjects with presumed eradication + Number of subjects with persistence + Number of subjects with presumed persistence)

Microbiological response definitions of superinfection and new infection are presented in Table 7 below:

Term Definition	
Superinfection	Isolation of a non-baseline pathogen from blood or respiratory cultures while the subject is on test article and the subject shows progression or development of new symptoms of CABP or development of infectious complications of CABP (ie, the subject is deemed a clinical failure by the investigator at the EOT Visit)
New infection	Isolation of a non-baseline pathogen from a post-treatment culture of a blood or respiratory specimen and the subject shows progression or development of new symptoms of CABP or development of infectious complications of CABP (ie, the subject is deemed a clinical failure by the investigator at the PTE Visit)

Table 7.	Microbiological Response De	finitions: Superinfection or New Infection
----------	-----------------------------	--

Abbreviations: CABP = community-acquired bacterial pneumonia.

For subjects with multiple microbiological samples taken either while the subject is on test article (for determination of superinfection) or post-treatment (for determination of new infection) all cultures will be used in the analysis.

5.3 Safety Measures

The safety parameters include AEs, clinical laboratory evaluations, vital signs, and electrocardiogram (ECG) findings. AEs will be coded using the Medical Dictionary of Regulatory Activities (MedDRA, Version to be delineated in the CSR) to the System Organ Class and Preferred Term levels.

5.4 Pharmacokinetic Parameters

The concentration of omadacycline will be obtained from plasma samples. Refer to the pharmacokinetic analysis plan for further details.

6 ANALYSIS POPULATIONS

6.1 Analysis Populations

6.1.1 Intent-to-Treat (ITT) Population

The ITT population will consist of all randomized subjects regardless of whether or not the subject received test article. A subject is considered randomized when the IxRS provides the test article assignment (ie, completes a randomization transaction).

6.1.2 Safety Population

The Safety population will consist of all randomized subjects who receive test article (either active or placebo). All safety analyses will be conducted in this population.

6.1.3 Microbiological Intent-to-Treat (microITT) Population

The microITT population will consist of all subjects in the ITT population who have at least one causative bacterial pathogen identified from a culture of a respiratory specimen (eg, respiratory fluid obtained by bronchoalveolar lavage [BAL] or bronchoscopy; pleural fluid obtained by thoracentesis; or expectorated or induced sputum meeting adequacy criteria as defined by the Gram stain results), culture of blood or from a culture-independent method (eg, positive urinary antigen test for *Streptococcus pneumoniae* or *Legionella pneumophila*, or positive serology for *Legionella pneumophila*, *Mycoplasma pneumoniae*, or *Chlamydophila pneumoniae*) at baseline.

Pathogen determination of typical bacteria is based on the genus and species identification from the central laboratory. If the local laboratory grows an acceptable pathogen but the central laboratory is not able to grow the isolate, if isolates are lost during transportation or storage, or there are major discrepancies between the local and central laboratory in the identification of species, the central laboratory or other Sponsor designee will request that the local laboratory resend the isolate. If the central laboratory cannot determine the genus and species of the isolate for any reason, the local laboratory determination of genus and species will be used for pathogen identification. The central laboratory identification of genus and species is used for analysis unless no central determination exists in which case the local laboratory determination is used.

In general, baseline is defined as the 24-hour period prior to the administration of the first dose of test article. However, if the subject is unable to produce a sputum sample at baseline or the sputum sample is not adequate based on the Gram stain criteria, a specimen obtained within 24 hours after the first dose of test article may be considered a baseline sample. If the sputum sample collected in the 24-hour period prior to the administration of the first dose of test article is not adequate based on the Gram stain criteria and the sputum sample obtained within 24 hours after the first dose of test article is not adequate based on the Gram stain criteria and the sputum sample obtained within 24 hours after the first dose of test article is not adequate based on the Gram stain criteria and the sputum sample obtained within 24 hours after the first dose of test article is not adequate based on the Gram stain criteria and the sputum sample obtained within 24 hours after the first dose of test article is not adequate based on the Gram stain criteria, only the sputum sample collected in the 24-hour period prior to administration of the first dose of test article will be considered baseline. UAT samples up through 24 hours after the first dose of test article may be considered the baseline sample, if a previous sample was

not taken or was found to be negative. Blood samples up through 24 hours after the first dose of test article may be considered the baseline sample, if a previous sample was not taken or was found not to have a pathogen.

The following isolates will always be considered a pathogen:

Streptococcus pneumoniae

- Positive BAL, bronchoscopy, pleural fluid, or blood culture; or
- Positive sputum culture in the presence of an adequate Gram stain defined as having > 25 polymorphonuclear neutrophils (PMNs)/Low Power Field (LPF) and < 10 Squamous Epithelial Cells (SECs)/LPF; or
- Positive urinary antigen test

Haemophilus influenzae

- Positive BAL, bronchoscopy, pleural fluid, or blood culture; or
- Positive sputum culture in the presence of an adequate Gram stain (> 25 PMNs/LPF and < 10 SECs/LPF)

Staphylococcus aureus

- Positive BAL, bronchoscopy, pleural fluid, or blood culture
- Positive sputum culture in the presence of an adequate Gram stain (> 25 PMNs/LPF and < 10 SECs/LPF)

Moraxella catarrhalis

- Positive BAL, bronchoscopy, pleural fluid, or blood culture; or
- Positive sputum culture in the presence of an adequate Gram stain (>25 PMNs/LPF and < 10 SECs/LPF)

Legionella pneumophila

- Positive BAL, bronchoscopy, pleural fluid, or blood culture; or
- Positive sputum culture, regardless of Gram stain findings; or
- Positive or borderline acute (baseline) or positive or borderline convalescent (PTE) IgM (Euroimmun IgM ELISA IgM ≥0.80 ratio).
- Negative acute (baseline) and positive or borderline convalescent (PTE) IgG (Euroimmun IgG ELISA IgG ≥16 RE/mL).
- A positive urine antigen test

Mycoplasma pneumoniae

- Positive or borderline acute (Baseline) or positive or borderline convalescent (PTE) IgM (Euroimmun IgM ELISA IgM ≥0.80 ratio).
- Negative acute (Baseline) and positive or borderline convalescent (PTE) IgG (Euroimmun IgG ELISA IgG ≥16 RE/mL).

Chlamydophila pneumoniae

- Positive or borderline acute (Baseline) or positive or borderline convalescent (PTE) IgM (Euroimmun IgM ELISA IgM ≥0.80 ratio)
- Negative acute (Baseline) and positive or borderline convalescent (PTE) IgG (Euroimmun IgG ELISA IgG ≥16 RE/mL)

The following isolates are considered as contaminants from respiratory specimens rather than pathogens of CABP: *Candida* spp. and other fungi, *Enterococcus* spp., viridans streptococci, coagulase-negative staphylococci, *Micrococcus* spp., *Neisseria* spp. other than *N. meningitidis*, *Corynebacterium* spp. and other coryneforms, *Lactobacillus* spp., *Vibrio* spp., *Capnocytophaga* spp., *Cardiobacterium* spp., *Flavobacterium* spp, *Staphylococcus lugdunensis*, *Staphylococcus capitis*, *Staphylococcus capiter*, *Staphylococcus haemolyticus*, *Staphylococcus haemolyticus*, *Staphylococcus simulans*, *Streptococcus saprophyticus*, *Staphylococcus sciuri*, *Staphylococcus simulans*, *Streptococcus epidermidis*, *Streptococcus viridans*, *Staphylococcus warneri*, *Staphylococcus xylosus*

Other isolates identified from culture of blood and respiratory specimens will be reviewed in a blinded manner by the Sponsor on a case-by-case basis for determination of whether the organism is a pathogen for CABP.

Staphylococcus aureus will be considered a distinct pathogen with methicillin-resistant *Staphylococcus aureus* (MRSA) and methicillin-susceptible *Staphylococcus aureus* considered distinct pathogens. Likewise, *Streptococcus pneumoniae* will be a distinct pathogen with penicillin-nonsusceptible *Streptococcus pneumoniae*, penicillin-susceptible *Streptococcus pneumoniae*, quinolone-resistant *Streptococcus pneumoniae*, and multiple drug resistant *Streptococcus pneumoniae* each considered distinct pathogens. A pathogen will be considered multiple drug resistant if susceptibility testing shows resistance to one drug in 3 or more of the classes of antibiotics provided below except in the case of MRSA where penicillin and cephalosporin are due to a single mechanism in which case 2 non- β -lactam resistances in addition to oxacillin, will be considered multi-drug resistant. *Streptococcus* spp. and *Staphylococcus* spp., isolates resistant to macrolides but susceptible to lincosamides and D-test positive (> 4/0.5 ug/ml) will be considered resistant to both macrolides and lincosamides. Susceptibility will be based on the most current CLSI guidelines for each antibiotic or if unavailable, on FDA

labeled susceptibility criteria. Antibiotics that define resistance for the class are listed as follows:

- Penicillins penicillin
- Fluoroquinolones moxifloxacin
- Cephalosporins ceftriaxone
- Lincosamides clindamycin
- Macrolides azithromycin or erythromycin
- Tetracyclines tetracycline or doxycycline
- Folate Pathway Inhibitors Trimethoprim/sulfamethoxazole
- Glycopeptides vancomycin
- Oxazolidinone linezolid

If there are multiple specimens (of the same testing modality) from the same time-point where the same pathogen is isolated, only the pathogen with the highest MIC to the test article received will be used. If the pathogens have the same MIC to the test article received, the pathogen with the lowest accession number will be used. The Gram stain associated with the selected pathogen will be utilized for analysis.

If the same pathogen is identified from the blood and respiratory sample, for tables providing MIC or disk diffusion data, the pathogen with the highest MIC to the test article received will be used.

